Developed using Framingham Heart Study data,^{1,2} the Framingham Risk Score is an estimate of a subject's 10-year risk of developing CVD which is computed using sex-specific algorithms that contain the following risk factors: age, systolic blood pressure (SBP), smoking status, TC, HDL-C, treatment for hypertension, and diabetes status. Smoking status refers to cigarette smoking status and will be collected once for each subject during the study and recorded on the Medical History CRF. Specifically, a smoker is defined as a subject where smoking is recorded on the Medical History CRF with a start date on or before first dose (ie, smoking start date \leq day of first dose) and a stop date on or after first dose (ie, smoking stop date \geq day of first dose). Partial and missing dates will be imputed using rules in [Appendix 2](#). [Appendix 3](#) contains anatomical therapeutic chemical (ATC) categories and descriptions that will be used to identify treatment for hypertension. A subject is considered to be receiving treatment for hypertension at baseline if there is at least 1 treatment for hypertension with a start date on or before first dose (ie, medication start date \leq day of first dose) and a stop date on or after first dose (ie, medication stop date \geq day of first dose). Partial and missing dates will be imputed using rules in [Appendix 2](#). CVD comprises coronary death, myocardial infarction, coronary insufficiency, angina, ischemic stroke, hemorrhagic stroke, transient ischemic attack, peripheral artery disease, and heart failure. Please refer to [Appendix 4](#) for the sex-specific algorithms that will be used to compute each subject's Framingham Risk Score at baseline and Week 12.

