10.2 Demographics and Baseline Characteristics

Demographic information will be summarized using descriptive statistics by randomized treatment group and overall for the FAS. Additionally, demographic information will be presented by statin-intensity stratum (moderate and high), for diabetic subjects, and for subjects with and without mixed dyslipidemia. Explicitly, the following characteristics will be summarized:

- Sex (Male, Female);
- Menopausal Status for Females (post-menopausal or surgically sterile, pre-menopausal);
- Race (White, Black or African American, Asian, American Indian or Alaska Native, Native Hawaiian or Other Pacific Islander, Other);
- Ethnicity (Hispanic or Latino, Not Hispanic or Latino, Unknown);
- Age;
- Height;
- Weight; and
- BMI,

where age will be computed for each subject using the following formula:

$$\text{Age} = \text{integer} ([\text{Screening Visit date} - \text{date of birth}] / 365.25),$$

and BMI will be calculated using the following formula:

$$\text{BMI} = (\text{body weight in kilograms}) / (\text{height in meters})^2.$$

Pregnancy test results will be listed for female subjects.

Additionally, baseline primary and secondary endpoints along with 1 exploratory endpoint, C1 will be summarized for the FAS by randomized treatment group and overall. Specifically, the following parameters will be summarized at baseline: lipids, apolipoproteins, inflammatory biomarkers, and the Framingham Risk Score. This table will then be repeated for

each baseline statin-intensity stratum (moderate, high). Additionally, the number and percentage of diabetic subjects and subjects on and not on ezetimibe in each of the previously mentioned groups will be summarized for the FAS. A subject on ezetimibe is defined as a subject with ezetimibe recorded on the Concomitant Medications CRF with a start date on or before first dose (ie, medication start date \leq day of first dose) and a stop date on or after first dose (ie, medication stop date \geq day of first dose). Partial and missing dates will be imputed using rules in [Appendix 2](#).

Further, for the subgroup of diabetic subjects within the FAS, baseline fasting insulin, FPG, HbA1c, lipids, apolipoproteins, and inflammatory biomarkers will be summarized by randomized treatment group and overall.

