Framingham Risk Score at baseline and Week 12 along with CFBL in Framingham Risk Score to Week 12 will be summarized by randomized treatment group using descriptive statistics. Framingham Risk Score at baseline has been explicated previously. Framingham Risk Score at Week 12 will be computed for each subject using the following variables at the following time points: age at the Screening Visit, TC at Week 12, HDL-C at Week 12, SBP at Week 12, treatment for hypertension at Week 12, smoking status at Day 1, and diabetes status at the Screening Visit. A subject is considered to be receiving treatment for hypertension at Week 12 if there is at least one treatment for hypertension with a start date on or before their Week 12 Visit (last dose) (ie, medication start date \leq day of last dose) and a stop date on or after their Week 12 Visit (last dose) (ie, medication stop date \geq day of last dose). Partial and missing dates will be imputed using rules in [Appendix 2](#).

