13.2 Prior and Concomitant Medications

Prior and concomitant medications will be coded using the World Health Organization (WHO) Drug Dictionary version 01 Mar 2016. A prior medication is defined as a medication with a stop date prior to the date of the subject's first dose (ie, medication stop date < date of first dose). A concomitant medication is defined as a medication with a start date on or before the date of the subject's last dose (ie, medication start date \leq date of last dose) and a stop date on or after the date of the subject's first dose (ie, medication stop date \geq date of first dose); thus, a medication that is ongoing at the time of the subject's first dose is considered concomitant. Partial and missing dates will be imputed using rules in [Appendix 2](#).

Prior and concomitant medications will be summarized in separate tables and listings. Medications will be summarized by ATC level 3 (level 3 indicates the therapeutic/pharmacologic subgroup) alphabetically and preferred name (decreasing frequency in the Gemcabene column within each ATC) by actual treatment group for the SAS. At each level of summarization, subjects who report one or more medications within a given level (eg, ATC and preferred name) will only be counted once at that level. Excluded medications will be flagged in the concomitant medications listing.

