Appendix 2. Prior and Concomitant Medications and Smoking Status Date Imputation

Imputation Rules for Partial Dates (D = day, M = month, Y = year)			
Parameter	Missing	Additional Conditions	Imputation
Start date	D only	M and Y same as M and Y of first dose of study drug	Date of first dose of study drug
		M and/or Y not same as date of first dose of study drug	First day of month
	M and D	Y same as Y of first dose of study drug Y not same as Y of first dose of study drug	Date of first dose of study drug Use Jan 01 of Y
	M, D, and Y	None - date completely missing	Day prior to date of first dose of study drug
Stop date	D only	M and Y same as M and Y of last dose of study drug	Date of last dose of study drug
		M and/or Y not same as date of last dose of study drug	Last day of month
	M and D	Y same as Y of last dose of study drug Y not same as Y of last dose of study drug	Date of last dose of study drug Use Dec 31 of Y
	M, D, and Y	None - date completely missing and NOT ongoing	Date of last dose of study drug

Note: In all cases, if an estimated start date is after a complete stop date, use the first day of the stop date month.

Similarly, if the estimated stop date is before a complete or imputed start date, use the last day of the start day month.

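### When a stop date is partial and the start is missing (or known only as the first-dose year), SAP Appendix 2 overrides the recorded stop and can code a treatment that ended before the trial as concomitant and ongoing at baseline

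*SAP*

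**What the plan says.** The table in SAP Appendix 2 fills in partial dates.

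- A completely missing start becomes "Day prior to date of first dose of study drug".
- For a year-only start the two cells read "Date of first dose of study drug Use Jan 01 of Y": the first applies if the year is that of first dose, the second otherwise.
- A stop lacking only the day becomes "Last day of month", unless it falls in the month of last dose.
- A year-only stop becomes 31 December of that year, unless it is the year of last dose. In either exception the stop becomes the date of last dose.

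The Note under the table then settles conflicts in two ways. If the imputed start falls after a complete stop, the start yields and moves to the first day of the stop month. For a stop that was itself estimated, the rule is the reverse: "if the estimated stop date is before a complete or imputed start date, use the last day of the start day month".

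The resulting dates are used in several places.

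- Section 13.2 separates prior from concomitant medication by whether the stop precedes first dose, and adds: "Excluded medications will be flagged in the concomitant medications listing".
- Section 10.2: "A subject on ezetimibe is defined as a subject with ezetimibe recorded on the Concomitant Medications CRF", with dates spanning first dose.
- Section 6.2: "A subject is considered to be receiving treatment for hypertension at baseline if there is at least 1 treatment for hypertension", again with dates spanning first dose. Smoking status is defined the same way.
- Section 11.2: "A subject is considered to be receiving treatment for hypertension at Week 12 if there is at least one treatment for hypertension", with dates spanning last dose.
- Section 12.4 repeats the blood pressure summary by baseline antihypertensive status.

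**The concern.** The second half of the Note applies even when the start is imputed. A date created by rule then outranks a month or year that the site recorded. If that month or year lies before first dose, the record contradicts the source data and falls on the wrong side of the definition of prior medication in Section 13.2. Losing only the day of a known stop is enough to reverse the classification.

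The outputs at risk are the prior and concomitant tables, the excluded-drug flag, the ezetimibe count, two Framingham inputs (smoking and antihypertensive treatment), and blood pressure by antihypertensive status. The Framingham input matters most. The moved stop lies at the end of the first-dose month, so a past antihypertensive can read as on at baseline and off at Week 12, which is a change that never happened. Framingham change is a secondary endpoint, and the only cardiovascular-risk endpoint left after SAP Section 8 dropped the NCEP ATP-III category.

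**Working it through.** The plan gives no figure to reproduce, so the check applies the rule literally.

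**Worked records.** Calendar dates are illustrative: first dose 10 Apr 2017, last dose 3 Jul 2017 (first dose + 84 days, Day 85).

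| Recorded start | Recorded stop | After the table (start; stop) | After the Note | Class |
|---|---|---|---|---|
| unknown | 15 Feb 2012 | 9 Apr 2017; 15 Feb 2012 | 1 to 15 Feb 2012 | prior |
| unknown | Feb 2012 | 9 Apr 2017; 29 Feb 2012 | 9 to 30 Apr 2017 | concomitant, on at baseline |
| unknown | 2012 | 9 Apr 2017; 31 Dec 2012 | 9 to 30 Apr 2017 | concomitant, on at baseline |
| 2017 | 10 Feb 2017 | 10 Apr 2017; 10 Feb 2017 | 1 to 10 Feb 2017 | prior |
| 2017 | Feb 2017 | 10 Apr 2017; 28 Feb 2017 | 10 to 30 Apr 2017 | concomitant, on at baseline |
| 2016 | Mar 2016 | 1 Jan 2016; 31 Mar 2016 | no conflict | prior |
| Jun 2015 | Mar 2016 | 1 Jun 2015; 31 Mar 2016 | no conflict | prior |

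The last two rows show the limit of the fault: a start dated to an earlier month or year causes no conflict.

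**Exception.** If the start is missing and first dose is on the 1st of a month, the imputed start lies in the previous month. With first dose 1 Feb 2017 and stop Mar 2016, the stop moves to 31 Jan 2017. The date is wrong but the class stays prior.

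**Counts, given the combination.** All 365 first-dose dates of 2017 were taken, with last dose 84 days later.

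- Start missing, stop month 1 to 24 months before the first-dose month: 365 − 12 = 353 dates misclassify; 353 × 24 = 8472 of 365 × 24 = 8760 (96.7%).
- Start missing, stop known only as a year from 2005 to 2016: 353 × 12 = 4236 of 4380 (96.7%).
- Start given as the first-dose year, stop in an earlier month of that year: summing days in month × (month number − 1) gives 2017 combinations (the match with the calendar year is chance), and all 2017 misclassify.

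**Baseline versus Week 12.** None of the month-level cases counts as on therapy at last dose. The moved stop is at most about a month after first dose, while a completer's last dose is about 12 weeks after it.

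**Illustrative Framingham size.** Appendix 4 gives risk as one minus baseline survival raised to a hazard term. If treated status multiplies the hazard by k, a risk p becomes 1 − (1 − p)^k. I found no coefficients there, so k and p are assumptions. With p = 15%:

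- k = 1.2: 1 − 0.85^1.2 = 17.7%
- k = 1.5: 1 − 0.85^1.5 = 21.6%
- k = 1.8: 1 − 0.85^1.8 = 25.4%

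The false fall by Week 12 is therefore 2.7 to 10.4 points for one affected subject who takes no other antihypertensive. In an arm of 52, one such subject moves the mean by 2.7/52 = 0.05 to 10.4/52 = 0.20 points.

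**The case against.** The strongest reply is that the trigger is narrow and the outputs are minor. Much of that stands.

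- **Scope.** A reader might infer that drugs stopped before the trial are generally coded concomitant. They are not. The fault needs a partial stop together with a start that is missing or known only as the first-dose year.
- **Frequency.** The 97% and 100% figures might be read as shares of records. They are shares of calendar dates once that combination exists, and the documents do not say how often it does. Protocol Section 5.6.4 asks for medications from informed consent onward, wash-out begins at a study visit (Section 6.2), and missing data are queried (Section 10.1.5). Long-stopped drugs may therefore be rare in the data, and washed-out drugs will probably have complete stop dates. Smoking history is a likelier source of old partial dates. A former smoker with unknown start and only a quitting year would be coded a current smoker. That status enters both Framingham scores, so it distorts their level without creating an on-to-off switch.
- **Reach.** A reader might suppose that the main result or the Per-Protocol Set is compromised. The primary ANCOVA (SAP 11.1) uses none of these dates. Nothing in SAP 7.1.2 ties exclusion from the PPS to the listing flag. The ezetimibe efficacy analyses were dropped (SAP Section 8), and Framingham is summarised descriptively (SAP 11.2).

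What the reply does not remove is the contradiction itself. I found no passage that limits the second half of the Note or protects a recorded stop month or year.

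**Conclusion.** Wrong as written, with low impact. Within its narrow trigger the rule replaces recorded information with an invented date. It misclassifies the record in every case examined except a missing start with first dose on the 1st of a month. For a 12-week completer on no other antihypertensive, it can also manufacture a stop in treatment between baseline and Week 12.

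The consequences are confined to descriptive secondary, baseline and safety outputs. The mechanism follows from the SAP text alone. The calendar dates are illustrative, the number of affected records is unknown, and the 2.7 to 10.4 point range depends wholly on an assumed hazard multiplier and a 15% risk. It should not be read as an estimate of bias in the endpoint.

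**What to change.** Limit the second sentence of the Note to start dates that are complete or have a recorded month, and add:

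> If the start date is completely missing or year-only and its imputed value is after an imputed stop date, keep the recorded stop month or year and set the start to the first day of the recorded stop month (1 January of the recorded stop year if only the year is known), but never before the recorded start year; query records whose recorded years conflict. A record whose recorded stop month or year ends before first dose is prior.

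Letting the start yield in this way brings the misclassified cases in the enumeration to 0 of 8760 (start missing, month-level stop) and 0 of 2017 (year-only start).

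The limit to starts without a recorded month is essential. If every imputed start yielded, a drug recorded as starting in July 2017 and stopping in 2017, with last dose on 20 June 2017, would have its start moved to 1 January 2017. It would become concomitant and on at baseline. The present Note moves that stop to 31 July and correctly leaves the drug non-concomitant.

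The cost is a short edit to Appendix 2 and a small change to the date program. No data collection or subject is affected. A count of records with this date pattern would show whether any output changes.

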Appendix 3. ATC Categories and Descriptions of Hypertensive Treatments

The WHO Drug Dictionary version 01 Mar 2016 was used to identify the following ATC categories and descriptions which will be used to identify hypertensive treatment.

ATC2/ATC2 Description ¹	ATC3/ATC3 Description	ATC4/ATC4 Description
C02/ANTIHYPERTENSIVES	C02A/ ANTIADRENERGIC AGENTS, CENTRALLY ACTING	C02AA/ Rauwolfia alkaloids
C02/ANTIHYPERTENSIVES	C02A/ ANTIADRENERGIC AGENTS, CENTRALLY ACTING	C02AB/Methyldopa
C02/ANTIHYPERTENSIVES	C02A/ ANTIADRENERGIC AGENTS, CENTRALLY ACTING	C02AC/Imidazoline receptor agonists
C02/ANTIHYPERTENSIVES	C02B/ANTIADRENERGIC AGENTS, GANGLION-BLOCKING	C02BA/Sulfonium derivatives
C02/ANTIHYPERTENSIVES	C02B/ANTIADRENERGIC AGENTS, GANGLION-BLOCKING	C02BB/Secondary and tertiary amines
C02/ANTIHYPERTENSIVES	C02B/ANTIADRENERGIC AGENTS, GANGLION-BLOCKING	C02BC/Bisquaternary ammonium compounds
C02/ANTIHYPERTENSIVES	C02C/ANTIADRENERGIC AGENTS, PERIPHERALLY ACTING	C02CA/Alpha-adrenoreceptor antagonists
C02/ANTIHYPERTENSIVES	C02C/ANTIADRENERGIC AGENTS, PERIPHERALLY ACTING	C02CC/Guanidine derivatives
C02/ANTIHYPERTENSIVES	C02D/ARTERIOLAR SMOOTH MUSCLE, AGENTS ACTING ON	C02DA/Thiazide derivatives
C02/ANTIHYPERTENSIVES	C02D/ARTERIOLAR SMOOTH MUSCLE, AGENTS ACTING ON	C02DB/Hydrazinophthalazine derivatives
C02/ANTIHYPERTENSIVES	C02D/ARTERIOLAR SMOOTH MUSCLE, AGENTS ACTING ON	C02DC/Pyrimidine derivatives
C02/ANTIHYPERTENSIVES	C02D/ARTERIOLAR SMOOTH MUSCLE, AGENTS ACTING ON	C02DD/Nitroferricyanide derivatives
C02/ANTIHYPERTENSIVES	C02D/ARTERIOLAR SMOOTH MUSCLE, AGENTS ACTING ON	C02DG/Guanidine derivatives
C02/ANTIHYPERTENSIVES	C02K/OTHER ANTIHYPERTENSIVES	C02KA/Alkaloids, excl. rauwolfia
C02/ANTIHYPERTENSIVES	C02K/OTHER ANTIHYPERTENSIVES	C02KB/Tyrosine hydroxylase inhibitors
C02/ANTIHYPERTENSIVES	C02K/OTHER ANTIHYPERTENSIVES	C02KC/MAO inhibitors
C02/ANTIHYPERTENSIVES	C02K/OTHER ANTIHYPERTENSIVES	C02KD/Serotonin antagonists
C02/ANTIHYPERTENSIVES	C02K/OTHER ANTIHYPERTENSIVES	C02KW/Herbal antihypertensives, other
C02/ANTIHYPERTENSIVES	C02K/OTHER ANTIHYPERTENSIVES	C02KX/Antihypertensives for pulmonary arterial hypertension
C02/ANTIHYPERTENSIVES	C02L/ANTIHYPERTENSIVES AND DIURETICS IN COMBINATION	C02LA/Rauwolfia alkaloids and diuretics in combination
C02/ANTIHYPERTENSIVES	C02L/ANTIHYPERTENSIVES AND DIURETICS IN COMBINATION	C02LB/Methyldopa and diuretics in combination
C02/ANTIHYPERTENSIVES	C02L/ANTIHYPERTENSIVES AND DIURETICS IN COMBINATION	C02LC/Imidazoline receptor agonists in combination with diuretics

C02/ANTIHYPERTENSIVES	C02L/ANTIHYPERTENSIVES AND DIURETICS IN COMBINATION	C02LE/Alpha-adrenoreceptor antagonists and diuretics
C02/ANTIHYPERTENSIVES	C02L/ANTIHYPERTENSIVES AND DIURETICS IN COMBINATION	C02LF/Guanidine derivatives and diuretics
C02/ANTIHYPERTENSIVES	C02L/ANTIHYPERTENSIVES AND DIURETICS IN COMBINATION	C02LG/Hydrazinophthalazine derivatives and diuretics
C02/ANTIHYPERTENSIVES	C02L/ANTIHYPERTENSIVES AND DIURETICS IN COMBINATION	C02LK/Alkaloids, excl. rauwolfia, in combination with diuretics
C02/ANTIHYPERTENSIVES	C02L/ANTIHYPERTENSIVES AND DIURETICS IN COMBINATION	C02LL/MAO inhibitors and diuretics
C02/ANTIHYPERTENSIVES	C02L/ANTIHYPERTENSIVES AND DIURETICS IN COMBINATION	C02LN/Serotonin antagonists and diuretics
C02/ANTIHYPERTENSIVES	C02L/ANTIHYPERTENSIVES AND DIURETICS IN COMBINATION	C02LX/Other antihypertensives and diuretics
C02/ANTIHYPERTENSIVES	C02N/COMBINATIONS OF ANTIHYPERTENSIVES IN ATC-GR. C02	-
C03/DIURETICS	C03A/LOW-CEILING DIURETICS, THIAZIDES	C03AA/Thiazides, plain
C03/DIURETICS	C03A/LOW-CEILING DIURETICS, THIAZIDES	C03AB/Thiazides and potassium in combination
C03/DIURETICS	C03A/LOW-CEILING DIURETICS, THIAZIDES	C03AH/Thiazides, combinations with psycholeptics and/or analgesics
C03/DIURETICS	C03A/LOW-CEILING DIURETICS, THIAZIDES	C03AX/Thiazides, combinations with other drugs
C03/DIURETICS	C03B/LOW-CEILING DIURETICS, EXCL. THIAZIDES	C03BA/Sulfonamides, plain
C03/DIURETICS	C03B/LOW-CEILING DIURETICS, EXCL. THIAZIDES	C03BB/Sulfonamides and potassium in combination
C03/DIURETICS	C03B/LOW-CEILING DIURETICS, EXCL. THIAZIDES	C03BC/Mercurial diuretics
C03/DIURETICS	C03B/LOW-CEILING DIURETICS, EXCL. THIAZIDES	C03BD/Xanthine derivatives
C03/DIURETICS	C03B/LOW-CEILING DIURETICS, EXCL. THIAZIDES	C03BK/Sulfonamides, combinations with other drugs
C03/DIURETICS	C03B/LOW-CEILING DIURETICS, EXCL. THIAZIDES	C03BX/Other low-ceiling diuretics
C03/DIURETICS	C03C/HIGH-CEILING DIURETICS	C03CA/Sulfonamides, plain
C03/DIURETICS	C03C/HIGH-CEILING DIURETICS	C03CB/Sulfonamides and potassium in combination
C03/DIURETICS	C03C/HIGH-CEILING DIURETICS	C03CC/Aryloxyacetic acid derivatives
C03/DIURETICS	C03C/HIGH-CEILING DIURETICS	C03CD/Pyrazolone derivatives
C03/DIURETICS	C03C/HIGH-CEILING DIURETICS	C03CX/Other high-ceiling diuretics
C03/DIURETICS	C03D/POTASSIUM-SPARING AGENTS	C03DA/Aldosterone antagonists
C03/DIURETICS	C03D/POTASSIUM-SPARING AGENTS	C03DB/Other potassium-sparing agents

C03/DIURETICS	C03E/DIURETICS AND POTASSIUM-SPARING AGENTS IN COMBINATION	C03EA/Low-ceiling diuretics and potassium-sparing agents
C03/DIURETICS	C03E/DIURETICS AND POTASSIUM-SPARING AGENTS IN COMBINATION	C03EB/High-ceiling diuretics and potassium-sparing agents
C03/DIURETICS	C03X/OTHER DIURETICS	C03XA/Vasopressin antagonists
C03/DIURETICS	C03X/OTHER DIURETICS	C03XW/Herbal diuretics, other
C07/BETA BLOCKING AGENTS	C07A/BETA BLOCKING AGENTS	C07AA/Beta blocking agents, non-selective
C07/BETA BLOCKING AGENTS	C07A/BETA BLOCKING AGENTS	C07AB/Beta blocking agents, selective
C07/BETA BLOCKING AGENTS	C07A/BETA BLOCKING AGENTS	C07AG/Alpha and beta blocking agents
C07/BETA BLOCKING AGENTS	C07B/BETA BLOCKING AGENTS AND THIAZIDES	C07BA/Beta blocking agents, non-selective, and thiazides
C07/BETA BLOCKING AGENTS	C07B/BETA BLOCKING AGENTS AND THIAZIDES	C07BB/Beta blocking agents, selective, and thiazides
C07/BETA BLOCKING AGENTS	C07B/BETA BLOCKING AGENTS AND THIAZIDES	C07BG/Alpha and beta blocking agents and thiazides
C07/BETA BLOCKING AGENTS	C07C/BETA BLOCKING AGENTS AND OTHER DIURETICS	C07CA/Beta blocking agents, non-selective, and other diuretics
C07/BETA BLOCKING AGENTS	C07C/BETA BLOCKING AGENTS AND OTHER DIURETICS	C07CB/Beta blocking agents, selective, and other diuretics
C07/BETA BLOCKING AGENTS	C07C/BETA BLOCKING AGENTS AND OTHER DIURETICS	C07CG/Alpha and beta blocking agents and other diuretics
C07/BETA BLOCKING AGENTS	C07D/BETA BLOCKING AGENTS, THIAZIDES AND OTHER DIURETICS	C07DA/Beta blocking agents, non-selective, thiazides and other diuretics
C07/BETA BLOCKING AGENTS	C07D/BETA BLOCKING AGENTS, THIAZIDES AND OTHER DIURETICS	C07DB/Beta blocking agents, selective, thiazides and other diuretics
C07/BETA BLOCKING AGENTS	C07E/BETA BLOCKING AGENTS AND VASODILATORS	C07EA/Beta blocking agents, non-selective, and vasodilators
C07/BETA BLOCKING AGENTS	C07E/BETA BLOCKING AGENTS AND VASODILATORS	C07EB/Beta blocking agents, selective, and vasodilators
C07/BETA BLOCKING AGENTS	C07F/BETA BLOCKING AGENTS AND OTHER ANTIHYPERTENSIVES	C07FA/Beta blocking agents, non-selective, and other antihypertensives
C07/BETA BLOCKING AGENTS	C07F/BETA BLOCKING AGENTS AND OTHER ANTIHYPERTENSIVES	C07FB/Beta blocking agents, selective, and other antihypertensives
C08/CALCIUM CHANNEL BLOCKERS	C08C/SELECTIVE CALCIUM CHANNEL BLOCKERS WITH MAINLY VASCULAR EFFECTS	C08CA/Dihydropyridine derivatives
C08/CALCIUM CHANNEL BLOCKERS	C08C/SELECTIVE CALCIUM CHANNEL BLOCKERS WITH MAINLY VASCULAR EFFECTS	C08CX/Other selective calcium channel blockers with mainly vascular effects
C08/CALCIUM CHANNEL BLOCKERS	C08D/SELECTIVE CALCIUM CHANNEL BLOCKERS WITH DIRECT CARDIAC EFFECTS	C08DA/Phenylalkylamine derivatives

C08/CALCIUM CHANNEL BLOCKERS	C08D/SELECTIVE CALCIUM CHANNEL BLOCKERS WITH DIRECT CARDIAC EFFECTS	C08DB/Benzothiazepine derivatives
C08/CALCIUM CHANNEL BLOCKERS	C08E/NON-SELECTIVE CALCIUM CHANNEL BLOCKERS	C08EA/Phenylalkylamine derivatives
C08/CALCIUM CHANNEL BLOCKERS	C08E/NON-SELECTIVE CALCIUM CHANNEL BLOCKERS	C08EX/Other non-selective calcium channel blockers
C08/CALCIUM CHANNEL BLOCKERS	C08G/CALCIUM CHANNEL BLOCKERS AND DIURETICS	C08GA/Calcium channel blockers and diuretics
C09/AGENTS ACTING ON THE RENIN-ANGIOTENSIN SYSTEM	C09A/ACE INHIBITORS, PLAIN	C09AA/ACE inhibitors, plain
C09/AGENTS ACTING ON THE RENIN-ANGIOTENSIN SYSTEM	C09B/ACE INHIBITORS, COMBINATIONS	C09BA/ACE inhibitors and diuretics
C09/AGENTS ACTING ON THE RENIN-ANGIOTENSIN SYSTEM	C09B/ACE INHIBITORS, COMBINATIONS	C09BB/ACE inhibitors and calcium channel blockers
C09/AGENTS ACTING ON THE RENIN-ANGIOTENSIN SYSTEM	C09B/ACE INHIBITORS, COMBINATIONS	C09BX/ACE inhibitors, other combinations
C09/AGENTS ACTING ON THE RENIN-ANGIOTENSIN SYSTEM	C09C/ANGIOTENSIN II ANTAGONISTS, PLAIN	C09CA/Angiotensin II antagonists, plain
C09/AGENTS ACTING ON THE RENIN-ANGIOTENSIN SYSTEM	C09D/ANGIOTENSIN II ANTAGONISTS, COMBINATIONS	C09DA/Angiotensin II antagonists and diuretics
C09/AGENTS ACTING ON THE RENIN-ANGIOTENSIN SYSTEM	C09D/ANGIOTENSIN II ANTAGONISTS, COMBINATIONS	C09DB/Angiotensin II antagonists and calcium channel blockers
C09/AGENTS ACTING ON THE RENIN-ANGIOTENSIN SYSTEM	C09D/ANGIOTENSIN II ANTAGONISTS, COMBINATIONS	C09DX/Angiotensin II antagonists, other combinations
C09/AGENTS ACTING ON THE RENIN-ANGIOTENSIN SYSTEM	C09X/OTHER AGENTS ACTING ON THE RENIN-ANGIOTENSIN SYSTEM	C09XA/Renin-inhibitors

ATC = anatomical therapeutic chemical, MAO = monoamine oxidase, ACE = angiotensin-converting enzyme

¹ All medications listed have ATC1/ATC1 Description=C/CARDIOVASCULAR SYSTEM.

